GCS Co., Ltd.	GANA X® CIP #21E0805	Final version 3.0 Date: 07/04/2022	Page 1/5
---------------	-------------------------	---------------------------------------	----------

SUMMARY OF THE CLINICAL INVESTIGATION PLAN # 21E0805

ANSM registration #:	2021-A02728-33
Clinical investigation plan #:	21E0805
Title of the clinical investigation:	CLINICAL STUDY FOR THE EFFECTIVENESS OF USE OF AN INJECTABLE MEDICAL DEVICE GANA X® IN THE TREATMENT OF BUTTOCKS VOLUME DEPRESSION
Sponsor:	GCS Co., Ltd. [name]
Development phase	Post market study Interventional Device used according to Instruction For Use (IFU)
Objectives:	
The primary objective is to evaluate the effectiveness of Gana X® in improving buttocks volume 6 months after treatment.
 
The secondary objectives of the study are:
 
 - to evaluate the effectiveness of Gana X® in improving buttocks volume 1½, 9, 12, 18 and 24 months after treatment. - to evaluate the effectiveness of Gana X® on the global aesthetic improvement of buttocks 1½, 6, 9, 12, 18, 24 months after treatment as rated by the evaluator. - to evaluate the effectiveness of Gana X® on the global aesthetic improvement of buttocks 1½, 6, 9, 12, 18, 24 months after treatment as rated by the subjects. - To evaluate the subject satisfaction with Gana X® 1½, 6, 9, 12, 18 and 24 months after treatment. - To evaluate the injector satisfaction with Gana X® after initial and touch-up injection if applicable. - To evaluate the safety of Gana X®.
Design:	The study will be: 
 • In open, • Single center.
Planned Sample Size:	55 subjects included.
Number of investigational study sites:	1 site (France).
Inclusion criteria:	
 1. Healthy Subject. 2. Sex: male or female. 3. Age: between 18 and 65 years. 4. Subject with mild to moderate buttock volume depression and/or seeking buttocks volume augmentation based on investigator evaluation. 5. Subject willing to abstain from other body contouring procedures during the whole study period. 6. Subject psychologically able to understand the study related information and to give a written informed consent. 7. Subject having given freely and expressly his/her informed consent. 8. Subject willing to have photographs taken.

GCS Co., Ltd.	GANA X® CIP #21E0805	Final version 3.0 Date: 07/04/2022	Page 2/5

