Endpoints:	
Primary effectiveness endpoint: Mean change in buttocks volume from baseline to 6 months after treatment using fringe projection system.
 
Secondary effectiveness endpoints:
 
 - Mean change in buttocks volume from baseline to 1^{1/2}, 9, 12, 18 and 24 months after treatment using fringe projection system. - GAIS responder rates 1^{1/2}, 6, 9, 12, 18 and 24 months after treatment as assessed by an independent live evaluator. A responder is defined as a subject having "Improved", "Much improved" or "Very much improved" score according to GAIS. - GAIS responder rates 1^{1/2}, 6, 9, 12, 18 and 24 months after treatment as assessed by the subjects. - Proportion of satisfied subjects 1^{1/2}, 6, 9, 12, 18 and 24 months after treatment using a questionnaire. - Injector's satisfaction regarding injection quality after initial and touch-up injection using a questionnaire. 
Secondary safety endpoints: Investigational device safety will be assessed by collection of Injection Site Reactions (ISRs) and Adverse Events (AEs) throughout

GCS Co., Ltd.	GANA X® CIP #21E0805	Final version 3.0 Date: 07/04/2022	Page 4/5
---------------	-------------------------	---------------------------------------	----------

	
the study by the investigator. Subjects will record ISRs and AEs in their subject diaries.

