Study Procedures:	
A screening visit will allow to inform and preselect the subjects.
 
On D0, fringe projection acquisitions and photographs will be done before injection. Eligible subjects will receive a first injection of the investigational device. Immediately after injection, injector's treatment satisfaction will be collected. Investigator evaluator will collect AEs and ISRs immediately after injection.
 
A month and a half after initial injection (M1^{1/2}), GAIS scoring, fringe projection acquisitions and photographs will be done before touch-up injection (if applicable). A touch-up injection will be made if necessary, according to injector and subject opinion. Investigator evaluator will collect AEs and ISRs before and after touch-up if applicable. Subject's treatment satisfaction and injector's treatment satisfaction (if applicable) will be collected.
 
Six (M6), nine (M9), twelve (M12), eighteen (M18) and twenty-four (M24) months after initial injection, effectiveness scoring (GAIS scale), fringe projection acquisitions and photographs will be done. Subject's treatment satisfaction will be collected. Investigator evaluator will collect AEs and ISRs

Statistical methods:	
For the primary evaluation criterion:
 
The primary endpoint is the mean change in buttocks volume from baseline to 6 months after treatment using fringe projection system. Descriptive statistics for quantitative data (N, mean, standard deviation, minimum and maximum) will be presented at D0 before injection and M6.
 
Inferential analysis:
 
A Wilcoxon signed rank test, or a paired t test will be applied to evaluate the change from baseline (D0 before injection) to M6. The normality assumption will be tested using a Shapiro Wilk test ($\alpha=0.01$). The bilateral approach will be used.
 
For the secondary evaluation criteria:
 
All the variables will be described using adapted statistics according to their type (quantitative data or qualitative data). For quantitative data a Wilcoxon or paired t test will be applied to assess the change from baseline.
 
The bilateral approach will be used with a significance level of 0.05.

Foreseen study duration:	
Clinical investigation beginning: Q1 2022
 
Clinical investigation end: Q3 2024
 
Inclusion duration: Maximum 6 months
 
Clinical investigation global duration: 30 months
 
Duration by subject: 24 months + screening period

FLOW-CHART

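### The five secondary volume tests each run at two-sided 0.05 with no gate on the M6 primary and no rule for concluding how long the gain lasts: a cheap improvement, not an error in the primary

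*Combined protocol and SAP*

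**What the plan says.** All references are to the combined protocol and SAP, a summary of the clinical investigation plan.

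- **Endpoints, primary:** "Mean change in buttocks volume from baseline to 6 months after treatment using fringe projection system". No other primary endpoint is named.
- **Endpoints, secondary:** "Mean change in buttocks volume from baseline to 1^{1/2}, 9, 12, 18 and 24 months after treatment using fringe projection system". The Objectives row also lists improvement at each of these five visits among the secondary objectives.
- **Statistical methods, primary criterion:** "A Wilcoxon signed rank test, or a paired t test will be applied to evaluate the change from baseline (D0 before injection) to M6". The test is two-sided. This paragraph gives no significance level for it.
- **Statistical methods, secondary criteria:** "For quantitative data a Wilcoxon or paired t test will be applied to assess the change from baseline", followed by "The bilateral approach will be used with a significance level of 0.05".
- **Planned Sample Size:** "55 subjects included", without power, effect size, SD or dropout.

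No test is named for the GAIS responder rates or the satisfaction proportions, so the planned effectiveness inference consists of six volume tests: one primary and five secondary. The summary does not order the secondary tests, make them depend on M6, adjust their level or call them descriptive. It does not say what pattern of results would support a statement on duration.

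**The concern.** Each of the five secondary visits has its own objective and its own test at the full level. If M6 misses and, say, M9 reaches p<0.05, nothing in the text stops a report that effectiveness on volume was shown at nine months. With follow-up to M24, readers will also ask how long the gain lasts. If the answer is taken to be the last visit with p<0.05, that visit is chosen after the results are known, and the error rate of the choice is not the 5% of any single test.

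At stake are the claims made from the secondary visits. The M6 test itself is unaffected.

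**Working it through.** The plan states no familywise rate, and 55 has no derivation, so there is no figure of the plan's own to reproduce. The check asks how often chance alone would give the two results described above.

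**Inputs from the documents:** one primary and five secondary volume tests; two-sided 0.05 for the secondary tests (M6 is taken at the same level, which is inferred); 55 subjects; one D0 measurement shared by all visits.

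**Assumed:** the correlation ρ between the changes at any two visits. If the D0 and visit readings carry independent errors of equal variance σ² and nothing else varies, each change has variance 2σ² and any two changes have covariance σ², so ρ = σ²/2σ² = 0.5. Changes in a subject that persist across visits push ρ higher. I use 0.5, 0.7 and 0.9, with 0 as an outer bound.

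**Model:** write each visit's test statistic as Z = √ρ·U + √(1−ρ)·e, with U and e independent standard normal, and use critical value 1.96. Given U = u, define

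- p(u) = Φ((1.96 − √ρ·u)/√(1−ρ)), the chance that a visit shows no false gain;
- q(u) = Φ((−1.96 − √ρ·u)/√(1−ρ)), the chance that it shows a false loss.

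With φ the standard normal density:

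- A: M6 not significant and at least one of five secondary visits shows a false gain = ∫ [p − q]·[1 − p⁵]·φ du.
- B: no true gain at M12, M18 or M24, and at least one shows a false gain = 1 − ∫ p³·φ du.

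By hand at ρ = 0, where p = 0.975 and q = 0.025: A = 0.95 × (1 − 0.975⁵) = 0.95 × 0.1189 = 11.3%, and B = 1 − 0.975³ = 7.3%. Numerical integration gives the rest:

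| ρ | A: M6 misses, false secondary gain | B: false gain at M12, M18 or M24 |
|---|---|---|
| 0 | 11.3% | 7.3% |
| 0.5 | 7.9% | 6.3% |
| 0.7 | 5.7% | 5.5% |
| 0.9 | 2.9% | 4.2% |

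A simulation of 100,000 trials with 55 subjects and paired t tests, counting M6 as missed when it shows no significant gain, gives 7.9%, 5.9% and 3.0% for A at ρ = 0.5, 0.7 and 0.9. The normal approximation is adequate.

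**With a gate and fixed order (M6, M9, M12, M18, M24):** A is zero by construction. For B, a claim at M12 or later first requires a false gain at M12 itself, so the rate is at most 0.05/2 = 2.5%.

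**Cost of splitting alpha instead:** Bonferroni over the five secondary tests gives 0.05/5 = 0.01 each. With 55 evaluable subjects and 80% power, the detectable standardised change rises from (1.960 + 0.842)/√55 = 0.38 SD to (2.576 + 0.842)/√55 = 0.46 SD. A gate avoids that loss.

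**The case against.** The strongest reply is that the plan is already clear about what counts. M6 is the only primary endpoint and has its own analysis paragraph, and the other visits are labelled secondary throughout. A reader might infer that a secondary visit may replace a failed primary. The documents do not say so, and the primary needs no correction for the secondary tests. That stands: the exposure is to selective reporting that the text does not rule out.

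A reader might also infer that a duration statement would have no error control at all. That is too strong. Each test holds its own 5% level, a conclusion tied in advance to M24 alone has 5% error, and one that requires significance at every visit needs no adjustment. The documents make no duration claim. What they lack is familywise control and a rule fixed beforehand.

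A third tempting figure is the chance that any of the six tests is significant under no change, 20.7% at ρ = 0.5. It counts false losses and the M6 test itself, neither of which can rescue a missed primary. Nor does it contradict a stated figure, because the plan's 0.05 is a per-test level.

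Two further points have weight. This is an open, single-centre, post-market study with no control arm described, so gating would not make a change from baseline attributable to the device. And the text is a summary, so fuller statistical wording may exist elsewhere. Both argue for modest severity; neither supplies the missing rule.

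**Conclusion.** The point holds as a cheap improvement. The five secondary volume tests have no gate, no familywise control and no duration rule, so an effectiveness claim at another visit after M6 misses is not prevented. With no true change, the chance of that combination is about 3% to 8% for ρ from 0.9 down to 0.5. For a gain that has gone by M12, a false late gain appears in about 4% to 6% of trials, against a 2.5% ceiling with a fixed order.

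These sizes rest on an assumed equal correlation between visits, on a two-sided 0.05 test at M6, on all 55 subjects contributing at every visit, and on one volume value per subject per visit. The flow chart lists two acquisition areas without saying how they are combined; testing them separately would add to the number of tests. The late figure also assumes no true gain at any of M12, M18 and M24.

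**What to change.** In Statistical methods, secondary evaluation criteria, add for volume:

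> Volume change at M6 is the primary test, two-sided at 0.05. Secondary volume tests support a claim only if M6 shows a significant gain. M9, M12, M18 and M24 are then tested in that order, each two-sided at 0.05; formal claims stop at the first visit without a significant gain. The duration conclusion is the last visit passed. M1½ and any visit after the stop are reported as estimates with 95% confidence intervals and nominal p-values.

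M1½ is left out of the sequence because it is measured before any touch-up and cannot speak to duration. The same edit should state the level for the primary test explicitly and how the two areas form one volume value.

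The cost is one paragraph. No data are added, the sample size and the M6 test are unchanged, and no alpha is split. The downside is that a chance miss at one visit ends formal claims at later ones, and M1½ has no confirmatory test.

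If the sponsor does not want a sequence, the minimum is a sentence stating that secondary p-values are descriptive and that no effectiveness or duration claim follows if M6 misses.

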Exclusion criteria:	
1. Pregnant or nursing woman or having given birth within the last year or planning a pregnancy during the study.
 
2. Excessive subcutaneous fat in the area to be treated.
 
3. Excessive skin laxity on the area to be treated.
 
4. Severe buttocks ptosis.
 
5. Subject who had been deprived of their freedom by administrative or legal decision or who is under guardianship.
 
6. Subject in a social or sanitary establishment
 
7. Subject participation to another research on human beings or who is in an exclusion period of one.
 
8. Subject having already received 4500 euros indemnities for participation in research involving human beings in the 12 previous months or exceeding these 4500 euros with his participation in the present study.
 
9. Subject suspected to be non-compliant according to the investigator's judgment.
 
10. Subject suffering from a severe or progressive disease or any other pathology that may interfere with the evaluation of the study results.
 
11. Subject with known history of or suffering from autoimmune disease and/or immune deficiency.
 
12. Subject with a history of cellulitis, streptococcal disease, such as acute rheumatic fever or recurrent sore throats and in case of acute rheumatic fever with heart complications.
 
13. Subject suffering from inflammatory and/or infectious cutaneous disorders in or near the studied zones (e.g. acne, chronic eczema, atopic dermatitis...).
 
14. Subject with an abscess, unhealed wound, or a cancerous or precancerous lesion on the studied zone.
 
15. Subject prone to develop inflammatory skin conditions or having tendency to bleeding disorders.
 
16. Subject with a tendency to develop keloids or hypertrophic scarring.
 
17. Subject with significant scarring, open wounds, lesions or tattoos in or near the area to be treated.
 
18. Subject having history of allergy or anaphylactic shock including hypersensitivity to Poly-l-lactic acid, to lidocaine or to one of the components of the tested devices or antiseptic solution.
 
19. Subject having received a dose of COVID-19 vaccine within the 14 days prior to injection visits or planning to receive a dose in the 14 days following injections.
 
20. Subject having received treatment on or near the buttocks (laser, dermabrasion, surgery, radiofrequency, cryolipolysis, buttocks electrostimulation, endermologie, liposuction, other energy-based treatment, surgery...) within the 12 months prior to screening visit.
 
21. Subject having received injection with a resorbable filling product in or near the buttocks within the 12 months prior to screening visit.
 
22. Subject having received at any time the following treatments in the area to be treated:
 
 • Buttocks implants;

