
GCS Co., Ltd.	GANA X® CIP #21E0805	Final version 3.0 Date: 07/04/2022	Page 3/5
---------------	-------------------------	---------------------------------------	----------

	
 • Buttocks fillers (e.g., silicone, semi-permanent or permanent fillers or autologous fat injections); • Injections for the treatment of cellulitis. 
23. Subject having started or changed her oral contraceptive or any other hormonal treatment during 12 weeks prior to screening visit.
 
24. Subject using medication such as aspirin, nonsteroidal anti-inflammatory drugs (NSAID) (ibuprofen, naproxen, ...), antiplatelet agents, anticoagulants or other substances known to prolong bleeding time within 1 week prior to injection visits.
 
25. Subject undergoing a topical treatment on the test area or a systemic treatment:
 
 • Antihistamines during the 2 weeks prior to injections visits (D0 and touch-up visit). • Immunosuppressors and/or corticoids during the 4 weeks prior to injections visits (D0 and touch-up visit). • Retinoids during the 6 months prior to injections visits (D0 and touch-up visit). 
26. Intensive exposure to sunlight or UV-rays within the month before injection visits and one month after.
 
27. Subject planning to loss or gain weight for the duration of the study.
 
28. Subject planning to change her/his life habits during the study.

Investigational device: Name / code Classification Ingredient Galenic form Administration route	Gana X® Class III medical device Poly-L-Lactic Acid (630mg), Sodium Carboxymethyl Cellulose, Mannitol. Sterile freeze-dried preparation (powder) Injection in the deep dermis and subcutaneous layer.

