Procedure	Visit 1 Screening	Visit 2 Day 0	Visit 3 M1 ^{1/2}	Visit 4 M6	Visit 5 M9	Visit 6 M12	Visit 7 M18	Visit 8 M24
Days	D-X	D0	D40 ± 2	D160 ± 4	D270 ± 4	D365 ± 7	D540 ± 14	D730 ± 14
Informed consent form signature	●							
Medical examination	●							
Medical history and previous and concomitant treatments collection	●							
Checking of the inclusion and exclusion criteria	●							
Pregnancy test		● ^b	● ^b					
Confirmation of eligibility		● ^b						
Photographs		● ^b	● ^b	●	●	●	●	●
Fringe projection acquisitions (2 areas)		● ^b	● ^b	●	●	●	●	●
Injection + anaesthesia (if necessary)		●	● Touch up					
GAIS live assessment by an independent evaluator			● ^b	●	●	●	●	●
GAIS assessment by the subjects			● ^b	●	●	●	●	●
Subjective evaluation questionnaire for subjects			● ^b	●	●	●	●	●
ISR live assessment by an independent evaluator		● ^a	● ^{b+a}	●	●	●	●	●
ISR assessment by the subjects		Completed each day during 4 weeks after injection at home by the subject.						
Subjective evaluation questionnaire for injector		● ^a	● ^a					
AE and concomitant treatments and procedures collection	●	●	●	●	●	●	●	●
Study end								●

Keys: ^b: Before injection; ^a: After injection

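### Does the lack of a scheduled eligibility re-check before the touch-up injection leave its exclusion criteria unenforced?

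*Combined protocol and SAP*

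**What the plan says.** In the Combined protocol and SAP, four exclusion items reach beyond the first injection.

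- **Item 25** names the touch-up outright for each drug class, for example "Immunosuppressors and/or corticoids during the 4 weeks prior to injections visits (D0 and touch-up visit" and "Retinoids during the 6 months prior to injections visits (D0 and touch-up visit". Antihistamines carry a 2-week window in the same form.
- **Item 24** covers drugs that affect bleeding, ending "or other substances known to prolong bleeding time within 1 week prior to injection visits".
- **Item 19** begins "Subject having received a dose of COVID-19 vaccine within the 14 days prior to injection visits" and also covers doses planned for the 14 days after injections.
- **Item 26** reads "Intensive exposure to sunlight or UV-rays within the month before injection visits and one month after".

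The FLOW-CHART has two injection visits: D0 and Visit 3 (M1½, D40 ± 2). It marks the check of the criteria at screening only, and "Confirmation of eligibility" at D0 only, before injection. At Visit 3 it schedules a pregnancy test before injection, and it collects adverse events together with concomitant treatments and procedures.

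Under Study Procedures, eligibility is mentioned for the first injection: "Eligible subjects will receive a first injection of the investigational device". The touch-up is described separately: "A touch-up injection will be made if necessary, according to injector and subject opinion".

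**The concern.** Four criteria apply to a second injection about 40 days after the last scheduled eligibility step. A subject could start a corticosteroid, take an anti-inflammatory drug, be vaccinated or have heavy sun exposure in between, and the schedule shows no step at which the investigator re-applies the criteria. The text on the touch-up speaks of need and opinion and does not mention eligibility. The pregnancy test is repeated at Visit 3, which suggests that the authors knew status can change between injections and provided for only one criterion.

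The safety endpoints would be at stake. Injection site reactions and adverse events after a touch-up that should not have been given would enter the reported rates. With 55 subjects, each affected subject could shift a subject-level rate by up to 1/55 = 1.8 percentage points.

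**Working it through.** The plan gives no figure to reproduce. The check has two parts: whether D0 could stand in for a Visit 3 check, and whether the passages conflict.

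**1. What D0 can see.** Inputs are the touch-up day T = 40 ± 2, so D38 to D42 (FLOW-CHART), and the look-back lengths in the Exclusion criteria. A look-back of L days starts at T − L. Two lengths are assumptions: one month = 30 days and six months = 182 days.

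| Item | L (days) | Start of window, T = 38 to 42 | Visible at D0? |
|---|---|---|---|
| 24, bleeding-time drugs | 7 | D31 to D35 | none |
| 19, vaccine | 14 | D24 to D28 | none |
| 25, antihistamines | 14 | D24 to D28 | none |
| 25, immunosuppressors/corticoids | 28 | D10 to D14 | none |
| 26, sun/UV | 30 | D8 to D12 | none |
| 25, retinoids | 182 | D−144 to D−140 | up to D0 |

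For retinoids the part not visible at D0 is the last 38 to 42 days: 38/182 = 20.9% to 42/182 = 23.1% of the window. Item 26 also restricts the month after an injection, which bars exposure to about D30. That is a restriction and not an observation: D0 cannot record what happens later, so the whole pre-touch-up window counts as unseen. The D0 confirmation therefore cannot do the work of a Visit 3 check.

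**2. Whether the passages conflict.**

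- *Criteria against procedures.* Item 25 binds at the touch-up in so many words, and the plural in items 19, 24 and 26 naturally covers both injection visits. The sentence "A touch-up injection will be made if necessary, according to injector and subject opinion" says when a touch-up is wanted. It does not say that the criteria lapse, so the two can be followed together.
- *Criteria against flow-chart.* The flow-chart omits a repeated eligibility mark. It does not state that eligibility is settled for good at D0.
- *Route of detection at Visit 3.* The row for concomitant treatments and procedures is marked at this visit. It carries no before-injection or after-injection key at any visit, D0 included, so the missing key at Visit 3 does not show that the information is gathered too late. Adverse events share that row, and Study Procedures has them collected both before and after the touch-up. Study Procedures does not give the timing for concomitant treatments.

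**3. What is left, item by item.** Drug use under items 24 and 25 falls within concomitant treatments. A vaccine dose (item 19) plausibly does too. Sun or UV exposure (item 26) has no related Visit 3 entry.

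**The case for a change.** The strongest reply is that a rule with no scheduled step to apply it may not be applied. Data collection is not verification: a drug noted at Visit 3 need not be weighed before the needle goes in, and nothing on the page links that row to the touch-up. The plan does schedule a pre-injection repeat for pregnancy, and one more flow-chart mark would cost almost nothing.

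Part of this stands. The summary does not show how the touch-up restrictions are verified, and for item 26 it does not show where exposure would be recorded.

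The rest is weaker. A pregnancy test is a procedure and needs its own row, whereas asking about medication need not have one, so repeating the test does not show that other checks were left out. Nor would the record be blank: concomitant treatments are collected at Visit 3 and at every later visit. If dates of use are recorded, as is usual, an analyst can find touch-ups given inside a restricted window under items 24 and 25 and list them as deviations. Finally, this is a five-page summary, and a row missing from it is weak evidence that the investigator has no such step.

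**Conclusion.** No change to the plan follows. The flow-chart has been read correctly and the date arithmetic holds: five of the six look-back windows lie wholly after D0, and for retinoids about 21% to 23% does. But the passages are compatible. Followed as written, the plan already forbids a touch-up in a subject who meets one of these items, and the medication data needed to apply or audit most of them are scheduled at the same visit. This is missing detail that investigators and analysts can fill sensibly.

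Its size cannot be put as a number of subjects. Neither the touch-up rate nor the frequency of newly met criteria is given; the only bound is the 55 planned subjects. The primary endpoint, change in volume from baseline to M6, is not affected by anything shown here, and there is no evidence that the safety conclusions would be unsound.

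This rests on three assumptions: that the plural wording in items 19, 24 and 26 covers the touch-up, that concomitant treatments are recorded with dates, and that vaccine doses are recorded among them. Item 26 is the one residue without a data source at Visit 3, which is too little to call for an amendment.

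### After the touch-up, reactions that persist or begin after day 28 rest on recall for 86–98 days, because subject recording is scheduled for only 4 weeks and the next visit is M6

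*Combined protocol and SAP*

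**What the plan says.** The Endpoints section of the plan summary makes safety a secondary endpoint: "Investigational device safety will be assessed by collection of Injection Site Reactions (ISRs) and Adverse Events (AEs) throughout" the study, by the investigator. The next sentence adds a second source: "Subjects will record ISRs and AEs in their subject diaries". It sets no date on which the diary closes.

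The flow-chart gives the only stated schedule for the subject's part. Its row for ISR assessment by the subjects reads "Completed each day during 4 weeks after injection at home by the subject". The row "ISR live assessment by an independent evaluator" is marked at Day 0 after injection, at M1½ before and after injection, and at M6, M9, M12, M18 and M24. A separate row for AEs and concomitant treatments is marked at every visit.

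There are up to two injections, one at Day 0 and an optional second at M1½. Study Procedures says of the second: "A touch-up injection will be made if necessary, according to injector and subject opinion". The flow-chart shows no visit or call between M1½ and M6. Statistical Methods has no ISR-specific analysis; secondary variables are to be described according to their type.

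**The concern.** The two injections are followed by very different lengths of time without scheduled recording. After the first, the diary closes shortly before an evaluator sees the subject. After the touch-up, it closes about three months before anyone is scheduled to see the subject.

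Two kinds of reaction are affected. One is still present when the 4 weeks end: its later course and end date are not prospectively recorded. The other starts and resolves between the end of the diary and M6: it is in no scheduled diary entry and cannot be seen by the evaluator at M6. Both depend on the subject remembering the event, volunteering it or being asked, and dating it.

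Forgotten events lower the count of later reactions, and poorly dated ones blur onset and duration. The study is open and single-centre with no comparison group described, so there is no concurrent arm with the same under-recording against which to judge the result.

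**Working it through.** The plan states no figure for this gap, so there is none to reproduce. The check is arithmetic on the visit windows.

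**Inputs**
- Diary length: 4 weeks = 28 days after injection (flow-chart). The row does not say each injection. I read it that way because M1½ is also an injection visit.
- First injection: D0. Touch-up: D40 ± 2, so D38 to D42 (flow-chart, Visit 3).
- M6: D160 ± 4, so D156 to D164 (Visit 4).
- M12: D365 ± 7. M18: D540 ± 14. M24: D730 ± 14.

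**Formulas**
- Shortest interval = earliest day of the next visit − latest day of the previous visit.
- Longest interval = latest day of the next visit − earliest day of the previous visit.
- Time without scheduled recording = interval − 28, where a diary is running.

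**Results**

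| Period | Interval (days) | Less diary | No scheduled recording (days) |
|---|---|---|---|
| D0 injection to M1½ | 38 to 42 | 28 | 10 to 14 |
| Touch-up to M6 | 156 − 42 = 114 to 164 − 38 = 126 | 28 | 86 to 98 |
| M1½ to M6, no touch-up | 114 to 126 | 0 | 114 to 126 |
| M12 to M18 | 526 − 372 = 154 to 554 − 358 = 196 | 0 | 154 to 196 |
| M18 to M24 | 716 − 554 = 162 to 744 − 526 = 218 | 0 | 162 to 218 |

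After a touch-up the diary covers 28/126 = 22% to 28/114 = 25% of the time to M6.

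**Illustration (assumed dates).** A reaction lasting from day 45 to day 85 after the touch-up starts 45 − 28 = 17 days after the diary ends. It resolves 114 − 85 = 29 days before the earliest possible M6 visit. No scheduled diary day covers it and it is not visible at M6. It enters the data only if it is reported at the M6 collection, or if the subject wrote it down unprompted.

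**What one missed event is worth.** Among the 55 planned subjects, one subject wrongly counted as free of later reactions moves the rate by 1/55 = 1.8 percentage points. The number who will have a touch-up is not given. Within that subset the step would be at least as large.

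**The case against.** **Collection does continue.** A reader might infer that stopping at 4 weeks contradicts collection throughout the study. It does not. That phrase describes collection by the investigator, and Study Procedures and the flow-chart place AE and ISR collection at M6 and every visit after it. A reaction that has resolved can be reported at M6, and one still present is seen. This stands: the issue is reliance on recall, not certain loss.

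**The diary may already be open-ended.** The Endpoints sentence has no time limit, and the flow-chart row may restrict only the daily scoring. That reading is possible. The text does not say so, however, and it leaves the subject's task after week 4 unclear. The document is also a summary, so a fuller diary instruction may exist that is not in the text supplied.

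**Touched-up subjects are not the least observed.** A reader might infer that those who have two injections have the longest unobserved stretch. The table shows otherwise: subjects without a touch-up have 114–126 days without scheduled recording over the same period, and all subjects have longer intervals between visits after M12. What distinguishes the touch-up gap is that it closely follows an injection.

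**No bias has been demonstrated.** A reader might infer that the safety result will look better than it is, or that a planned duration or first-versus-touch-up analysis is compromised. The documents give no rate of late or persistent reactions and describe neither analysis. Incomplete recall would tend to lower the count, but by how much, if at all, cannot be said.

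**Conclusion.** The point holds as a gap in coverage that is cheap to close. For 86–98 days after the touch-up diary ends, against 10–14 days after the first, no prospective recording of reactions is scheduled. Reactions that persist past day 28, or come and go before M6, may be under-recorded or misdated. The direction of error is likely to be towards fewer recorded later reactions; its size is unknown.

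This rests on three assumptions: the 4-week diary applies after each injection, visits fall within their stated windows, and no fuller diary instruction exists in the complete plan. If such an instruction already keeps the diary open after week 4, only the summary wording needs aligning.

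This is an improvement to the recording of a secondary safety endpoint. It does not touch the primary endpoint.

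**What to change.** Reconcile the diary sentence in Endpoints with the flow-chart row for ISR assessment by the subjects:

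- Keep the daily diary for 4 weeks after each injection.
- Have subjects then keep the same diary, at least to M6, for event-triggered entries only: any new ISR or AE with start and stop dates, and any reaction still open at day 28 until it ends.
- Review the diary with the subject at the M6 visit.
- If ISR duration is reported, show reactions unresolved at the last record as ongoing (censored), not as ending at day 28.

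The cost is a few diary pages and one instruction to subjects. No visit, test or staff is added. The burden is slight and falls mainly on subjects who have a reaction. The change does not shorten the later intervals between visits, and entries made only when something happens are less complete than daily ones. It reduces the reliance on recall after the touch-up but does not remove it.
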